If subject was not previously in XOLARIS study, BCVA assessments at baseline must be performed in triplicate.

For all subjects who require triplicate BCVA testing, to facilitate the additional BCVA measures, this visit should be conducted over 2 days, with BCVA measured twice on Day 1 and once on Day 2 (prior to pupil dilation). All 3 BCVA values must be recorded in the eCRF. The highest score will be used to define subject eligibility.

- 3. Assessments at screening collected in triplicate. To facilitate triplicate testing, the visit should be conducted over 2 days. Visual field and microperimetry outputs will be sent to a CRC for review. Data will be generated and collated within the CRC and exported to the Sponsor or designee. For microperimetry, the last assessment performed during screening will be used for assessing eligibility and will be defined as the baseline assessment.
- 4. Octopus 900 perimeter is specified for visual field assessments only in Part II.

Subjects who meet all the inclusion criteria and none of the exclusion criteria will have a study eye assigned and be enrolled into the study. In Part II, subjects will be informed of the randomisation outcome (i.e., AAV8-RPGR treatment or the Control group) and instructed to not reveal their treatment group assignment to the masked assessors during the study. Subjects randomised to the AAV8-RPGR treatment groups (along with the Investigators and sponsor) will remain masked to the assigned dose.

See Section 8.5 for details on randomisation and assignment of subject numbers.

The next study visit (Visit 2) is to be scheduled within 12 weeks of the Screening/Baseline Visit. Subjects will be given a course of oral prednisone/prednisolone and instructed to start taking the drug 2 days (Part I) or 3 days (Part II) before their next study visit (Visit 2). Where applicable, subjects will also be instructed to use barrier contraception or abstain from sexual intercourse for a period of 3 months from the time they are treated.

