12.6. Efficacy Analyses

Efficacy assessments are ocular in nature and therefore will be tabulated by eye (Study Eye and Fellow Eye). In Part I, efficacy endpoints will be summarised on observed data using descriptive statistics only (described in Section 12.4). In Part II, efficacy endpoints will be summarized on observed data using descriptive statistics. Additional analyses for handling missing data will be provided for the primary endpoint and selected secondary endpoint.

For each subject, data collected within 6 months of the last visit window will be included in the primary analysis, as described in greater detail in the SAP.

At final analysis in Part II, the primary endpoint, which is defined as the proportion of study eyes with ≥7 dB improvement from baseline at ≥5 of the 16 central loci at 12 months, will be compared between treatment groups (high dose vs untreated; low dose vs untreated) using the Fisher Exact-Boschloo test with a Berger-Boos correction of beta=0.001 (Berger and Boos 1994). The CIs for the difference in proportions between treatment groups will be presented by Miettinen and Nurminen (Miettinen and Nurminen 1985) method.

For the continuous variables of mean sensitivity, BCVA, and LLVA in Part II, the primary analysis to handle missing data uses a mixed model repeated measures (MMRM) model. The mean change from baseline will be analyzed using fixed effects of treatment group, study visit, study-visit-treatment interaction, and baseline value.

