7.12 Efficacy Analysis

7.12.1 General consideration

In Part I, efficacy endpoints will be performed using the Safety Analysis Set. For efficacy endpoints, observations collected within 6 months of the last visit window will be included in analysis. Efficacy endpoints will be summarized on observed data by descriptive statistics only. No imputation will be performed.

In Part II, efficacy endpoints will be performed using the ITT Analysis Set. For efficacy endpoints, observations collected within 6 months of the last visit window will be included in analysis.

For efficacy analysis of study eyes in Part II, descriptive analyses will be provided. Additional analyses for handling missing data will be also provided for the primary endpoint and selected secondary endpoints. For the primary endpoint regarding the proportion of eyes with improved retinal sensitivity, the primary analysis to handle missing data is the last observation carried forward (LOCF) on locus level. Then the imputed value will be dichotomized for analysis based on the responder criteria. The supplementary analyses include the non-responder imputation (NRI) imputed on locus level, and multiple imputation on locus level followed by two-sample Binomial test.

For mean change from baseline in mean sensitivity, the primary analysis to handle missing data is multiple imputation on locus level followed by the mixed model repeated measure (MMRM) analysis. For selected secondary endpoints (BCVA and LLVA) regarding their change from baseline, the primary analysis of handling missing data is the MMRM analysis. For other continuous endpoints, summaries will be made by descriptive only.

For efficacy analysis of fellow eyes in Part II, only descriptive analysis will be provided.

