Although the risk is low, to mitigate this risk a sensitivity analysis will be implemented by excluding mean sensitivity data assessed by unmasked assessor at Part II, Month 12. The sensitivity analysis will be applied to the summaries for the proportion of eyes with mean sensitivity ≥ 7 db improvement from baseline at ≥ 5 of the 16 loci at Month 12. The sensitivity analyses will be descriptive only and analyzed on observed case. For microperimetry data in Part II, the main analysis is still based on ITT analysis set. The

sensitivity analysis will be compared with the main analysis to assess the robustness of the data.

Exploratory analysis

Secondary Endpoint:

The secondary endpoint is the change from baseline in mean sensitivity of the 16 central loci and 68 whole loci at 1, 2, 3, 6, 9 and 12 months. Observed data collected within 6 months outside the last visit window will be used regardless of intercurrent events, i.e. discontinuation of study early or lost to follow up. Observed value and change from baseline will be summarized by treatment groups, visits and eyes. The CI for observed value will be provided based on one-sample t-test, and the CI for change from baseline will be provided by paired t-test. The difference of change from baseline between treatment and control group at each visit will be provided. The CI and p-value for the difference will be also provided, which are calculated based on two sample t-test.

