The primary analysis for handling missing data will be conducted by applying multiple imputation on each locus level, followed by the MMRM model under the assumption of MAR. Each imputed data set will use MMRM model to analyse change from baseline of the mean sensitivity, using fixed effects of treatment groups (high dose, low dose, and untreated), study visit, study visit-by-treatment interaction, baseline value of mean sensitivity and baseline-by-visit interaction. An unstructured covariance matrix will be used to model the within-patient variance-covariance errors. If the unstructured covariance structure matrix results are in a lack of convergence, the heterogeneous Toeplitz covariance structure followed by the heterogeneous first-order autoregressive covariance structure will be used. The Kenward-Roger approximation will be used to estimate the denominator degree of freedom. Results from analysis of each imputed dataset, i.e., least square (LS) mean differences from placebo and their SEs, will be combined using Rubin's method [Rubin 1987] as implemented in the proc mianalyze procedure to produce a pooled LS mean estimate of treatment difference, and its CI, and a nominal pooled p-value.

To account for microperimetry data from the one site impacted by unmasked assessments from month 3 to month 12, a sensitivity analysis will be implemented for central 16-loci mean sensitivity of observed value and change from baseline at Month 12, by excluding mean sensitivity data points assessed in an unmasked fashion at Month 12. The sensitivity analysis will be descriptive only and analyzed on observed case. The sensitivity analyses will be compared with analysis made by the ITT analysis set to assess the robustness of the data.

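### The observed-data comparison of change in mean sensitivity uses an unadjusted t-test; an ANCOVA on the baseline already collected would usually be more precise and would match the planned MMRM

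*SAP*

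**What the plan says.** SAP 7.12.2 defines the Part II secondary endpoint as "change from baseline in mean sensitivity of the 16 central loci and 68 whole loci at 1, 2, 3, 6, 9 and 12 months". Two between-group analyses of it follow.

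- **Observed data.** "Observed data collected within 6 months outside the last visit window will be used regardless of intercurrent events". The dose-minus-untreated difference in change is given at each visit, and "The CI and p-value for the difference will be also provided, which are calculated based on two sample t-test". No covariate is mentioned.
- **Imputed data.** SAP 7.12.1 says that for this endpoint "the primary analysis to handle missing data is multiple imputation on locus level followed by the mixed model repeated measure (MMRM) analysis". The model in 7.12.2 includes "baseline value of mean sensitivity and baseline-by-visit interaction", and results are pooled "to produce a pooled LS mean estimate of treatment difference, and its CI, and a nominal pooled p-value".

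Protocol 12.6 specifies only the model-based analysis for mean sensitivity, BCVA and LLVA: "The mean change from baseline will be analyzed using fixed effects of treatment group, study visit, study-visit-treatment interaction, and baseline value". It names no t-test. The baseline reading exists for this purpose; Protocol 9.1 says "the last assessment performed during screening will be used for assessing eligibility and will be defined as the baseline assessment".

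For change in BCVA (SAP 7.12.3), and by extension LLVA (7.12.4), the SAP plans descriptive summaries and a baseline-adjusted MMRM, with no between-group t-test. The unadjusted p-value is particular to mean sensitivity.

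**The concern.** With 6 visits, 2 grids and 2 doses, the t-test produces 6 × 2 × 2 = 24 unadjusted contrasts. Groups are about 10 v 9, and Protocol 8.5 describes blocked randomisation without stratification by baseline sensitivity, so some chance imbalance at baseline is to be expected. A change score corrects for that imbalance with a fixed slope of 1. If the true slope of follow-up on baseline is not 1, the contrast keeps a residual shift and loses precision.

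The second issue is interpretation. The observed-data result is a natural check on the imputed MMRM, but the two differ in missing-data handling and also in baseline adjustment. A gap between them could come from either. The SAP calls the MMRM primary only for handling missing data, so it does not say outright which p-value is to be interpreted.

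**Working it through.** **Inputs.** Group sizes of 10 and 9 are from SAP 6.6. The baseline-to-follow-up correlation rho and the SDs (s0 at baseline, s1 at follow-up) are not in the documents, so they are assumed over a range.

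**The plan's own figure.** The only stated power is about 87% for the binary primary endpoint (10 v 9, 50% v 5%, one-sided 0.10). Exact enumeration with the Boschloo test gives 86.8%, with or without the Berger-Boos correction. It reproduces, and this point does not touch it. No power is stated for mean sensitivity.

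**Chance imbalance.** The SD of the difference in baseline means is √(1/10 + 1/9) = 0.46 baseline SD.

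**General formulas.** Let b = rho·s1/s0 be the slope of follow-up on baseline.

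- ANCOVA residual variance: s1²(1 − rho²).
- Change-score variance: s0² + s1² − 2·rho·s0·s1 = s1²(1 − rho²) + (b − 1)²·s0².
- Before the cost of estimating the slope, the adjusted variance is therefore never larger. The gain is zero when b = 1.
- Conditional on the observed imbalance, the change-score contrast is shifted by (b − 1) × imbalance. A slope below 1 means over-correction and a slope above 1 means under-correction.

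**Equal SDs (s1 = s0).** Here b = rho, the variance ratio is (1 + rho)/2, and the shift has SD (1 − rho) × 0.46. Power is from a simulation at 10 v 9 (20,000 runs per setting, one-sided 0.10), with the effect set so that the t-test has about 80% power by the normal approximation.

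| rho | Variance ratio, adjusted/unadjusted | CI width ratio (before df cost) | SD of conditional shift (baseline SDs) | Power, t-test v ANCOVA |
|---|---|---|---|---|
| 0.3 | 0.65 | 0.81 | 0.32 | 78% v 88% |
| 0.5 | 0.75 | 0.87 | 0.23 | 78% v 85% |
| 0.7 | 0.85 | 0.92 | 0.14 | 79% v 82% |
| 0.9 | 0.95 | 0.97 | 0.05 | 79% v 79% |

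Simulated type I error was 0.097 to 0.103 across both methods. At rho 0.9 the small-sample cost of estimating the slope cancels the gain: the simulated SDs of the estimates under the null were 0.206 (t-test) and 0.207 (ANCOVA).

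**Unequal SDs (s1 = 1.5·s0).** The ratio is 2.25(1 − rho²)/(3.25 − 3·rho):

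- rho 0.3: 2.0475/2.35 = 0.87
- rho 0.5: 1.6875/1.75 = 0.96
- rho 0.7: 1.1475/1.15 = about 1.00 (b = 1.05)
- rho 0.8: 0.81/0.85 = 0.95 (b = 1.2, so the change score under-corrects)
- rho 0.9: 0.4275/0.55 = 0.78 (b = 1.35)

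At rho 0.5 the conditional shift falls to |0.75 − 1| × 0.46 = about 0.12 baseline SD. The gain is smaller than under equal SDs for rho up to 0.8. At 0.9 it is larger, because the slope has moved well above 1.

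**The case against.** The strongest reply is that the plan already contains the adjusted analysis. The MMRM gives a baseline-adjusted difference, CI and nominal p-value for the same contrast. With complete data, an unstructured MMRM with a baseline-by-visit term corresponds closely to an ANCOVA at each visit. Protocol 12.4 places formal testing on the primary endpoint, and the Hochberg procedure in SAP 7.5 covers only that endpoint. This stands and limits the severity. It does not remove the gain, because the observed-case interval and p-value will still be reported, and making them comparable with the MMRM is the point of having them.

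Three stronger readings are tempting, and the documents do not support them.

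- *All dose-v-untreated p-values for this endpoint are unadjusted.* They are not; the MMRM p-value is adjusted.
- *The t-test is biased, ignores baseline or always over-corrects.* It holds its level and is unbiased over randomisations. A change score does use baseline. The shift is conditional on the imbalance that occurs, and its direction depends on whether the slope is below or above 1.
- *The variance falls by a known amount.* The (1 + rho)/2 ratio needs equal SDs. There is reason to doubt that here: Protocol 7.2.1 restricts baseline mean sensitivity in the study eye to 0.1 to 8 dB, while follow-up is unrestricted.

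It is also fair to say that an ANCOVA leaves two p-values for each contrast. Replacing the test is therefore not enough, and the SAP should also say which result is for inference.

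**Conclusion.** The point holds as a low-severity improvement to a secondary endpoint. The observed-data t-test omits a covariate that the protocol and the SAP's own MMRM use for the same endpoint. At about 10 v 9 this usually costs precision and leaves the contrast sensitive to a chance baseline difference with SD 0.46 baseline SD.

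Under equal SDs, the t-test inflates variance by 2/(1 + rho) − 1: 54% at rho 0.3, 33% at 0.5, 18% at 0.7 and 5% at 0.9. If the follow-up SD is 1.5 times the baseline SD, the penalty is small for rho between 0.5 and 0.8. It is negligible wherever the slope is near 1. These sizes rest on assumed values of rho and of the SD ratio. A reader might infer that the trial's conclusion is at risk; it is not, because no power figure, alpha level or success criterion depends on this test.

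**What to change.** In SAP 7.12.2, replace the two-sample t-test with an observed-case ANCOVA at each visit: change = arm + baseline mean sensitivity on the same grid. Report the adjusted dose-v-untreated difference with an 80% CI, in line with the alpha of 0.20 in the SAP 7.16 code, and a nominal p-value. Add a sentence saying that the baseline-adjusted MMRM after multiple imputation is the result for inference and that the observed-case ANCOVA is supportive.

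The cost is SAP wording and one degree of freedom, with no new data. The ANCOVA also assumes a common linear slope, on a scale with a floor (SAP 7.12.2 scores readings below 0 as −1).

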7.16 Selected Algorithms/SAS Codes

• Descriptive statistics for continuous variables:

PROC UNIVARIATE DATA=dset NOPRINT; VAR var1 var2 var3 ...varn; BY byvar; (optional) OUTPUT OUT=outname N=n MEAN=mean MIN=min MAX=max MEDIAN=median STD=std P5=p5 P95=p95 Q1=q1 Q3=q3; RUN;

• 80% CIs for mean of observed (actual) value- one sample t-test:

proc ttest data=sample alpha=0.20; class treatment; var endpoint; run;

• 80% CIs for mean change from baseline- paired ttest formula:

```
proc ttest data=dset alpha = 0.20;
paired var1*var2;
run;
```

• Clopper-Pearson 80% CIs within group for binomial proportions:

proc freq data=one; tables response/binomial (exact) alpha=0.20 missprint; weight count; run;

• 80% CI for difference in proportion by the method of Miettinen and Nurminen

```
Proc freq data=dataset noprint;
tables group*outname/riskdiff(cl=mn) measure alpha = 0.20;
Output out = outname;
Run;
```

• Mixed Model Repeated Measures (MMRM)

Proc mixed DATA = data; CLASS subjid tr01pg1 visit; MODEL chg = tr01pg1 bs visit visit*tr01pg1 bs*visit / DDFM=KENWARDROGER Solution; REPEATED visit / TYPE=UN SUBJECT=subjid; LSMEANS visit*tr01pg1/cl pdiff; Run;

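### Pooled mean-sensitivity MMRM: the stated Rubin 1987 pooling does not carry the Kenward-Roger degrees of freedom forward, so CIs and nominal p-values come out slightly optimistic at N=29 (minor)

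*SAP*

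**What the plan says.** SAP 7.12.2 (Secondary Endpoint) names multiple imputation by locus followed by an MMRM as the main way of handling missing data for change in mean sensitivity. It applies to the 16 central loci and the full 68-locus grid.

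- **Model.** The fixed effects are treatment group, visit, their interaction, "baseline value of mean sensitivity and baseline-by-visit interaction".
- **Covariance.** "An unstructured covariance matrix will be used to model the within-patient variance-covariance errors". Heterogeneous Toeplitz and then heterogeneous first-order autoregressive structures are the fallbacks if the model does not converge.
- **Degrees of freedom in each imputed data set.** "The Kenward-Roger approximation will be used to estimate the denominator degree of freedom". The MMRM code in SAP 7.16 agrees: "MODEL chg = tr01pg1 bs visit visit*tr01pg1 bs*visit / DDFM=KENWARDROGER Solution".
- **Pooling.** The only inputs listed are the estimated differences and the standard errors from each fit. The rule is that these "will be combined using Rubin's method [Rubin 1987] as implemented in the proc mianalyze procedure to produce a pooled LS mean estimate of treatment difference". (The SAP calls the comparator placebo here; in Part II it is the untreated group.)
- **Output.** A pooled difference "and its CI, and a nominal pooled p-value".

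SAP 7.16 gives no PROC MIANALYZE code. Neither document states a complete-data degrees-of-freedom value, a Barnard-Rubin adjustment, the number of imputations, or the CI level for this analysis.

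**The concern.** Kenward-Roger makes two small-sample adjustments: it inflates the SE and it sets finite denominator degrees of freedom. As described, pooling receives the estimate and the SE only. Rubin's 1987 formula then creates its own degrees of freedom as if the complete-data sample were infinite.

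This has an odd consequence. As missing data vanish, the Rubin degrees of freedom go to infinity, so the pooled interval becomes narrower than the Kenward-Roger interval from the same data with nothing missing. Imputation should not add precision.

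At stake are the pooled CIs and nominal p-values for 2 grids × 6 visits × 2 doses = 24 contrasts. All are shifted in the same direction, towards narrower intervals and smaller p-values. The BCVA and LLVA models in SAP 7.12.3 and 7.12.4 are not multiply imputed, so they do not have this problem.

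**Working it through.** **Inputs**

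- Group sizes 10, 10 and 9, total 29. SAP 6.6 gives 10 per dose group and 9 untreated; the Version 11 amendment rationale gives 29.
- Mean parameters per visit: intercept, two treatment terms and baseline = 4 (SAP 7.12.2 model).
- Number of imputations m: not stated; assumed 5 to 100.
- Fraction of missing information λ: not stated; assumed 0.02 to 0.20.

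**The plan's own figure.** No degrees-of-freedom or pooled-CI figure is stated. The one power figure, about 87% for 10 against 9 (50% against 5%, Boschloo with Berger-Boos 0.001, one-sided 0.10), reproduces by exact enumeration at 86.8%. The group sizes can therefore be relied on.

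**Step 1, complete-data degrees of freedom.** Once imputation fills every visit, the unstructured MMRM with treatment-by-visit and baseline-by-visit terms is equivalent to a separate ANCOVA at each visit. The degrees of freedom are 29 − 4 = 25.

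**Step 2, limit of little missing data.** The Rubin reference becomes normal; the right one is t with 25 df.

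| Nominal CI | z | t(25) | Too narrow by 1 − z/t | True coverage |
|---|---|---|---|---|
| 80% | 1.282 | 1.316 | 2.6% | 78.8% |
| 95% | 1.960 | 2.060 | 4.8% | 93.9% |

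A reported two-sided p of 0.050 should be 0.061, and a one-sided 0.10 should be about 0.106.

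**Step 3, with missing data.** Let λ = (1 + 1/m)B/T, where B is the between-imputation variance and T the total variance.

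- Rubin 1987: ν = (m − 1)/λ².
- Barnard-Rubin: 1/ν* = 1/ν + 1/ν_obs, with ν_obs = (26/28) × 25 × (1 − λ).

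| m | λ | Rubin ν | Barnard-Rubin ν* | 80% CI ratio | 95% CI ratio |
|---|---|---|---|---|---|
| 5 | 0.02 | 10,000 | 22.7 | 0.971 | 0.947 |
| 5 | 0.20 | 100 | 15.7 | 0.964 | 0.934 |
| 20 | 0.05 | 7,600 | 22.0 | 0.970 | 0.945 |
| 20 | 0.10 | 1,900 | 20.7 | 0.968 | 0.942 |
| 100 | 0.20 | 2,475 | 18.4 | 0.964 | 0.935 |

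The ratio is the Rubin width over the Barnard-Rubin width. Inverting it, the corrected intervals are 1/0.971 − 1 = 3.0% to 1/0.964 − 1 = 3.7% wider at 80%, and 1/0.947 − 1 = 5.6% to 1/0.934 − 1 = 7.1% wider at 95%.

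**Step 4, does the correction restore the error rate?** Null simulation with arms of 9, 10 and 10, Month 12 imputed from arm, baseline and Month 9, and ANCOVA at Month 12. There were 4,000 runs per setting (1,500 at m=100).

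| Missing at Month 12 | m | Rubin, nominal 0.05 | Barnard-Rubin, nominal 0.05 |
|---|---|---|---|
| 0% | – | 0.056 (exact: 0.061) | 0.047 (exact: 0.050) |
| 10% | 20 | 0.059 | 0.045 |
| 20% | 20 | 0.059 | 0.049 |
| 20% | 5 | 0.061 | 0.050 |
| 20% | 100 | 0.058 | 0.043 |

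The Monte Carlo SE at 4,000 runs is √(0.05 × 0.95/4,000) ≈ 0.0034. A separate 4,000-run check at 10% missing and m=20 gave 5.7% and 4.2%. Across all simulation checks the ranges were about 5.0–6.7% with Rubin and 3.7–5.4% with Barnard-Rubin.

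The two references move further apart as λ rises, but the calibration gain does not grow with them. Barnard-Rubin turns slightly conservative, and the advantage fades by about 20% missing.

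**The case against.** The strongest case against is that this is an option left unspecified, in an analysis on which no decision rests.

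- **EDF= is not excluded.** The SAP says pooling is done as PROC MIANALYZE implements it, and EDF= belongs to that procedure. A reader might infer that the SAP orders the Kenward-Roger degrees of freedom to be thrown away. It does not say so. This stands, and it makes the point conditional on running the text as written. However, citing Rubin 1987 alone and listing only estimates and SEs points to the unadjusted form.
- **The small-sample protection is only partly lost.** The Kenward-Roger SEs do enter the pooling. This stands.
- **The 95% figures may not apply.** Part II intervals with a stated level are 80% (SAP 7.12.2 to 7.12.4 and 7.16), where the shortfall is smaller. The level here is not stated, so both are shown.
- **The correction is not perfectly calibrated.** In the separate check at 10% missing, the two rules miss 5% by about the same amount in opposite directions (+0.7 and −0.8 points). This stands.
- **A finite-df result is already planned.** SAP 7.12.2 also asks for a two-sample t-test CI and p-value for the difference at each visit on observed data.

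What remains is that the plan prescribes small-sample degrees of freedom and then describes a pooling rule that has no place for them.

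**Conclusion.** The point holds as a minor one. Run as written without EDF=, the pooled mean-sensitivity results are referred to an almost normal distribution when about 25 complete-data degrees of freedom exist. With little missing data the cost is 2.6% of width at 80% or 4.8% at 95%, and up to about one percentage point of two-sided type I error at 0.05, shrinking as missingness rises.

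This rests on four assumptions: all 29 subjects contribute, the unstructured fit converges, imputation completes every visit, and λ and m lie in the assumed ranges. A fallback covariance structure, or an exclusion under the SAP's extreme-outlier rule, would change the 25.

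A reader might go further and infer that the trial's efficacy conclusion is inflated. The documents do not support that. Study success depends only on the responder endpoint, tested by Boschloo's test under Hochberg (SAP 7.5), which uses no MMRM. The pooled p-value is labelled nominal and belongs to a secondary endpoint.

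**What to change.** Add to SAP 7.12.2 that pooled CIs and p-values use Barnard-Rubin degrees of freedom, with the Kenward-Roger degrees of freedom of each visit-by-dose contrast supplied to PROC MIANALYZE through EDF=. The value is about 25 under the unstructured fit with all 29 subjects; otherwise use the value from the fitted model. State the number of imputations and the CI level in the same place, and add the PROC MIANALYZE call to SAP 7.16 beside the MMRM code.

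The cost is a sentence or two of SAP text and one code option. Intervals become about 3–4% wider at 80% or 5–7% wider at 95%, with slight conservatism when more data are missing. No other analysis changes.
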